1 INTRODUCTION

1.1 Pruritus

Pruritus, or itch, is defined as an unpleasant sensation that evokes a desire to scratch (Ikoma 2006). Itch and pain, although closely related, are distinct sensations: itch elicits a scratching response, whereas pain causes a withdrawal response.

Emerging research in neurobiology has greatly expanded the understanding of pruritus signaling. Pruritoceptors (itch-sensory nerve fibers) consist of two distinct classes of nerve fibers: histamine-responsive mechanoinsensitive C-fibers, and histamine-unresponsive mechanosensitive polymodal C and Aδ fibers that are activated by cowhage (highly pruritic spicules from the pods of the cowhage plant *Mucuna pruriens*) (Schmelz 2015). The second class of histamine-unresponsive, cowhage-responsive nerve fibers has been of particular interest in pruritus research, as C-fibers that have a strong and sustained response to histamine comprise only about 20% of the overall mechanoinsensitive C-fiber population (Steinhoff 2006), and a significant proportion of chronic pruritic conditions do not appear to involve histamine-mediated pruritus signaling (Ikoma 2006). Substance P (SP) is a prominent pruritogen (itch mediator) in this histamine-independent pruritus pathway (Chuquilin 2016).

Pruritus stimuli in the skin are transmitted via sensory neurons that have their cell bodies in the dorsal root ganglia (DRG) and are linked to second-order neurons in the spine (Carstens 2016, Luo 2015). Following activation of these DRG sensory neurons, the pruritus signal is transmitted to the second-order spinal neurons primarily by SP, gastrin-releasing peptide, and glutamate in histamine-independent pruritus, and primarily by glutamate in histamine-mediated pruritus (Chuquilin 2016).

Spinal itch neuron projections ascend via the contralateral spinothalamic tract to the thalamus and via the lateral spinoparabrachial tract to the lateral parabrachial nucleus, from which point they activate multiple centers in the somatosensory cortex, the premotor cortex, and the cingulate cortex – areas involved in the sensory processing and motor response (scratching) to the itch signal (Carstens 2016, Chuquilin 2016).

1.1.1 Role of Substance P and the Neurokinin-1 Receptor in Pruritus

Substance P is an undecapeptide that belongs to the tachykinin family of neuropeptides, a group that also includes neurokinin A and neurokinin B (Hökfelt 2001). SP has been implicated in a number of biological functions, both physiological and pathophysiological, including pruritus perception, vomiting reflex, pain perception, and immunomodulatory responses (Lotts 2014, Andoh 1998, Steinhoff 2014). The biological actions of SP are mediated by tachykinin receptors, which consist of seven hydrophobic transmembrane domains coupled to G-proteins. Three tachykinin receptors have been identified: the neurokinin-1 (NK1-R), neurokinin-2, and neurokinin-3 receptors (Harrison 2001). The neurokinin-1 receptor, in particular, has been studied in great detail. NK1-R is the primary receptor for SP in the human body, and is found on multiple cell types, including central and peripheral neurons, keratinocytes, mast cells, and dendritic cells (E1-Nour 2006, Ständer 2015).

NK₁-R stimulation has been shown to be an important pathway for pruritus perception (Ständer 2015). Inhibition of this pathway results in decreased pruritus and scratching reflexes in animal models (Akiyama 2015). Preceding the development of seriopitant for pruritus-related conditions, a commercially available NK₁-R antagonist (Emend USPI) has been used as a therapy to decrease pruritus in patients with chronic pruritus due to etiologies such as cutaneous T-cell lymphoma (Duval 2009, Torres 2012, Booken 2011) and erlotinib-induced pruritus (Santini 2012, Gerber 2010). Additionally, in a study of 20 patients with chronic pruritus of various etiologies treated with aprepitant, 16/20 patients (80%) experienced a considerable reduction of itch intensity (Ständer 2010).

1.2 Serlopitant

1.2.1 Serlopitant Background and Nonclinical Summary

Serlopitant is a small molecule, highly selective NK₁-R antagonist that is administered orally and metabolized by cytochrome P-450 3A4 (CYP3A4), with a plasma half-life of 45-86 hours. It binds with high affinity to the human NK₁-R with a dissociation constant (Kd) of 46 pM; displacing SP binding with a half-maximal inhibition concentration (IC₅₀) of 61 pM. Serlopitant is a potent functional antagonist of SP-induced inositol phosphate generation.

Serlopitant has been extensively studied in animal toxicology studies, including chronic toxicology and carcinogenicity studies. In non-clinical chronic toxicology studies in rats, mice and dogs, treatment related findings of potential clinical significance included increased salivation, decreased body weight gain and food consumption, slight changes in hematology and serum biochemistry parameters, mild increases in liver weight and mild histomorphologic changes. The histomorphologic changes were seen only in rats (not in dogs or mice) and included: very slight ovarian interstitial cell hypertrophy, mammary gland and uterine atrophy; decreased corpora lutea; increased histiocytes in lung and mesenteric lymph nodes; slight skeletal and cardiac muscle degeneration; slight increased hematopoiesis in bone marrow; and slight to moderate vacuolation in kidney tubules. These nonclinical findings occurred at systemic exposures exceeding those anticipated to provide efficacy of serlopitant for pruritus indications in humans (1 to 5 mg tablet daily). No cardiac lesions have been observed in dog toxicity studies up to 9 months in duration nor in a 3-month mouse range-finding study and 2-year mouse carcinogenicity study at exposure higher than the lowest level which caused cardiotoxicity in rats. The no observed adverse effect level (NOAEL) in rats for histomorphological changes in the reproductive tract, mammary gland and bone marrow provides a 2.5-fold margin for the maximum-targeted exposure (5 mg tablet daily). The rat NOAEL for histomorphological changes in muscle and kidney provides a 5-fold margin for the maximum-targeted exposure (5 mg tablet daily).

In summary, the nonclinical toxicity noted with seriopitant provides no contraindications to the continuation of clinical trials via the oral route. Findings in the developmental toxicity studies support inclusion of women of childbearing potential in clinical trials in accordance with the study protocol and local regulatory guidances.

1.2.2 Serlopitant Clinical Summary

In humans, serlopitant has been administered to over 1000 individuals. Single doses up to 400 mg have been well tolerated in young adult males and single doses up to 25 mg have been well tolerated in the elderly. Multiple doses of up to 50 mg a day for 4 weeks have been well tolerated in healthy young males, and a single (loading) dose of 15 mg followed by daily doses of 5 mg for 2 weeks have been well tolerated in elderly males and females. Forty-one (41) subjects received 4 mg liquid filled capsule (LFC) daily (bioequivalent to 5 mg tablets) for 1 year. Plasma concentrations of serlopitant appear to increase in a dose-proportional fashion in both young males and elderly subjects (males and females). Peak plasma concentrations after a single oral dose occurred at \sim 2 to 4 hours in both young and elderly subjects. A single loading dose of up to 15 mg followed by 6 to 8 weeks of up to 5 mg daily doses has been well tolerated in adults with chronic pruritus and prurigo nodularis (PN).

Pharmacokinetic data demonstrate good plasma exposures with oral dosing, linear dosedependent increases in plasma concentration and systemic exposure, a plasma t1/2 appropriate for once daily dosing, and mild effects of concomitant food ingestion. Central nervous system (CNS) positron emission tomography (PET) studies have demonstrated good CNS penetrance and > 90% NK1 receptor occupancy (RO) at plasma exposures anticipated to be safe and well tolerated. Three long-lived active hydroxylated metabolites are observed in humans: M1/M1a CCI , M2/M2a CCI , and M3 CCI . These metabolites were present at lower concentrations and were 2- to 9-fold less potent in vivo than the parent compound. The integrated pharmacokinetic/pharmacodynamic (PK/PD) analysis concluded that these metabolites are unlikely to contribute significantly to occupancy of the CNS NK₁-R in humans.

1.2.3 Serlopitant in Pruritus-Related Studies

Serlopitant has been evaluated in two completed Phase 2 studies of subjects with chronic pruritus (TCP-101 and TCP-102).

TCP-101

TCP-101 was a double-blind, placebo-controlled, multi-center study that compared serlopitant 0.25 mg, 1 mg, or 5 mg vs. placebo for the treatment of chronic pruritus. A total of 257 adult subjects 18-65 years of age with chronic pruritus were randomized to receive one of the four dose groups in a 1:1:1:1 randomization. Subjects received a loading dose of 3 tablets on Day 1 and thereafter received 1 tablet per day for 6 weeks. The primary efficacy endpoint was itch severity as measured on a Visual Analog Scale (VAS), summarized as a percentage change from baseline.

Mean percent decreases from Baseline in VAS score were larger in the active-treatment groups versus placebo at every scheduled post-baseline study visit. Overall, the results were the most profound for the serlopitant 1 mg and 5 mg groups. For the percent change from Baseline in VAS pruritus scores (the primary efficacy variable), the Week 6 pairwise least squares mean difference compared to placebo was 5.8 mm, 13.2 mm, and 14.2 mm for serlopitant 0.25 mg, 1 mg, and 5 mg, respectively.

The frequency of treatment-emergent adverse events (TEAEs) and study drug related adverse events (AEs) was higher in the serlopitant 1 mg and 5 mg groups compared to the serlopitant 0.25 mg group, and the frequency in all three treatment groups were higher than in the placebo group. The frequency of AEs leading to study drug discontinuation was comparable in the serlopitant 5 mg and placebo group and higher than in the serlopitant 0.25 mg and 1 mg groups. There was one serious adverse event (SAE) reported in the serlopitant 1 mg group (spontaneous abortion, considered not related). There were no deaths. The most common AEs in the serlopitant groups were diarrhea (6.2%, 1 mg group), upper respiratory tract infection (4.7%, 0.25 mg group), somnolence (4.7%, 5 mg group), nasopharyngitis (4.6%, 1 mg group), headache (4.7%, 5 mg group), urinary tract infection (3.1%, 5 mg group), dry mouth (3.1%, 1 mg group), nausea (3.1%, 1 mg group), arthralgia (3.1%, 0.25 mg group), musculoskeletal pain (3.1%, 1 mg group) and pruritus (3.1%, 1 mg group). The most common AEs in the placebo group were headache (6.3%), nasopharyngitis (3.2%), upper respiratory tract infection (3.2%), urinary tract infection (3.2%).

TCP-102

TCP-102 was a randomized, double-blind, placebo-controlled multi-center study that evaluated seriopitant 5 mg vs. placebo for the treatment of PN A total of 128 adult subjects 18-80 years of age with PN were randomized to receive seriopitant or placebo in a 1:1 randomization. Subjects received a loading dose of 3 tablets on Day 1 followed by 1 tablet per day for 8 weeks. The primary efficacy endpoint was the average VAS score as recorded at the study visits. Results at Week 4 and Week 8 were the primary timepoints.

Serlopitant 5 mg was superior to placebo for the reduction of pruritus as measured by change in average VAS from baseline. For the primary endpoint, change from baseline at Week 4 and Week 8 by repeated measures analysis, the decrease from baseline was significantly greater in the serlopitant group than the placebo group, with a mean difference (serlopitant minus placebo) of -1.0 at Week 4 and -1.7 at Week 8. The mean difference at Week 2 was also significant, -0.9. In a post-hoc analysis of the percentage of subjects who were 4-point responders on average VAS at Week 8, 25.0% of placebo subjects and 54.4% of serlopitant subjects were 4-point responders.

TEAEs were reported for 71.9% of serlopitant-treated subjects and 61.9% of placebo-treated subjects. The most frequently reported TEAEs in the serlopitant group were nasopharyngitis (17.2% serlopitant, 3.2% placebo), diarrhea (10.9% serlopitant, 4.8% placebo), and fatigue (9.4% serlopitant, 6.3% placebo). Treatment-related TEAEs were reported for 48.4% of serlopitant-treated subjects and 34.9% of placebo-treated subjects. The most frequently reported treatment-related TEAEs in the serlopitant group were fatigue (7.8%) and diarrhea, peripheral edema, dizziness, and headache (each 6.3%). Most TEAEs were mild or moderate; severe TEAEs were reported for 9.4% of serlopitant-treated subjects and 4.8% of placebo-treated subjects. There were no deaths during the study. Five subjects (3 serlopitant, 2 placebo) had SAEs. The SAEs were actinic elastosis, depression, dizziness, and vertigo in the serlopitant group; and bradycardia, syncope, respiratory failure, and neurodermatitis in the placebo group. Nine subjects (3 serlopitant, 6 placebo) discontinued due to TEAEs.

No clinically relevant changes were observed in chemistry, hematology, vital signs, or electrocardiogram (ECG) results.

The results of the Phase 2 studies in PN and chronic pruritus, together with the extensive nonclinical and clinical safety data and experience with serlopitant to date and the scientific rationale for NK₁-R inhibition in the treatment of pruritus, serve to support further evaluation of serlopitant for the long-term treatment of pruritus in patients with PN, AD, or psoriasis. The potential benefits of continued clinical study outweigh the potential risks. The data obtained from this long-term study will inform the risks and benefits of long-term exposure (chronic or repeated intermittent use for longer than 6 months). The risk to subjects in this study will be minimized by medical and safety monitoring (see Section 3.4.1).

Please refer to the Investigator's Brochure for further information regarding seriopitant.

2 STUDY OBJECTIVES

The primary objective of this study is to assess the long-term safety of seriopitant in adults with pruritus associated with PN, AD, or psoriasis.

The secondary objectives of this study are to assess the change in severity of pruritus in subjects with PN, AD, or psoriasis using the worst-itch numeric rating scale (WI-NRS); to assess the change in severity and extent of PN using the Investigator's Global Assessment of PN Stage (IGA PN-S), for those subjects with PN; and to assess whether seriopitant produces physical dependence.

3 STUDY DESIGN

3.1 Overall Study Design

This is a multicenter, open-label study to assess the long-term safety of seriopitant in adults with pruritus associated with PN, AD, or psoriasis. Eligible subjects who have completed selected studies of seriopitant may be given the opportunity, at the investigator's discretion, to consent to and participate in this open-label study, regardless of their treatment allocation in prior studies. If deemed necessary by Menlo Therapeutics to meet enrollment objectives, eligible subjects who have not participated in a prior seriopitant study may also be enrolled in study MTI-107. Approximately 120 study sites may enroll subjects in this long-term safety study.

This study will consist of two periods, for a total study period of approximately 57 weeks:

- Treatment period: 52 weeks
- Post-drug observation period: 5 weeks

During the treatment period, subjects will take one seriopitant 5 mg tablet once daily orally (Section 5.3).

Standard therapy for the concurrent skin lesions and pruritus may be employed during this study (Section 5.7.1).

The WI-NRS during a 24-hour recall period will be assessed by the subject at each study visit.

For those subjects with PN, the severity and extent of PN will be assessed at selected visits, using the IGA-PN-S, and photographs of representative areas with PN will be taken at selected visits at a subset of sites.

The Dermatology Life Quality Index (DLQI) will be administered at selected visits.

After completion of the 52-week treatment period, all subjects will enter a 5-week post-drug observation period. Subjects who discontinue treatment early will have a post-drug observation visit through 5 weeks after their last dose of serlopitant. During this monitored discontinuation period, solicited safety evaluations will assess the potential for serlopitant to produce physical dependence.

3.2 Rationale for Study Design and Dose Selection

The current MTI-107 study is designed to confirm the long-term safety of seriopitant for the treatment of pruritus in patients with PN, AD, and psoriasis. The 5 mg dose of seriopitant was selected for this study based on the favorable efficacy, safety, and tolerability profile of seriopitant at this dose level in completed studies.

3.3 Study Endpoints

3.3.1 Safety Endpoints

The safety endpoints are as follows:

- Incidence of TEAEs and SAEs
- Change from baseline in clinical laboratory parameters
- Change from baseline in vital sign and ECG parameters
- Change from baseline in the Hospital Anxiety and Depression Scale (HADS)
- Change from baseline in the Epworth Sleepiness Scale (ESS)
- Assessment of physical dependence following chronic study drug exposure, in the 5-week post-drug discontinuation period.

3.3.2 *Efficacy Endpoints*

The efficacy endpoints are as follows:

- Change from baseline in WI-NRS to Weeks 4, 8, 20, 28, 36, 44, and 52
- Change from baseline in DLQI (symptoms and feelings, daily activities, leisure, work or school performance, personal relationships, and treatment) to Weeks 20, 36 and 52
- Change from baseline in IGA PN-S to Weeks 4, 8, 20, 28, 36, 44, and 52

3.4 Safety Review

3.4.1 Safety Monitoring Team

An internal safety monitoring team consisting of representatives from Menlo Therapeutics Inc. and its designees will monitor safety data on a regular basis throughout the study.

4 SELECTION OF STUDY POPULATION

4.1 Study Population

Up to 700 adult subjects with pruritus associated with PN, AD, or psoriasis will be enrolled in this study.

4.2 Inclusion Criteria

Subjects must meet the following criteria to be enrolled into the study:

- 1. Male or female, age 18 years or older at consent.
- 2. Subject reports pruritus in the 24-hour period prior to enrollment and:
 - a. Has completed a prior applicable clinical study of serlopitant without an SAE that was assessed as likely related to the study drug (For participants from study TCP-102, the WI-NRS score must be ≥ 7 in the 24-hour period prior to the Baseline visit.)

OR

- b. Has not participated in a prior clinical study of serlopitant and has a clinical diagnosis of PN, AD, or psoriasis, and has a WI-NRS score ≥ 7 in the 24-hour period prior to the Baseline visit, and Sponsor has approved enrollment.
- 3. All female subjects who are of childbearing potential must be willing to practice highly effective contraception (i.e., pregnancy prevention method with a failure rate of <1% per year, refer to Section 7.1.5 for acceptable methods of contraception) from the time of the Baseline visit until 5 weeks after last dose of study drug.
- 4. Willing and able (has adequate cognitive ability, in the investigator's opinion) to comply with study visits and study related requirements including providing written informed consent.
4.3 Exclusion Criteria

Subjects who meet any of the following criteria are not eligible for participation in the study:

- 1. Presence of malignancy within 5 years prior to enrollment (exception for non-melanoma cutaneous malignancies).
- 2. Any known major psychiatric diagnosis, such as major depressive disorder, bipolar disorder, schizophrenia, psychotic disorder, intellectual disability, severe alcohol use disorder, which may confound the assessment of serlopitant safety or efficacy, or interfere with the subject's ability to comply with protocol-mandated activities, within 3 years prior to enrollment.
- 3. Untreated or inadequately treated thyroid, adrenal, or pituitary nodules or disease, or history of thyroid malignancy; or the presence of any medical condition or disability, that, in the investigator's opinion, could interfere with the assessment of safety in this study or compromise the safety of the subject.
- 4. Treatment with any investigational therapy within 4 weeks or 5-half-lives prior to enrollment (whichever is longer) or expected participation in another clinical study involving an investigational product or device during the subject's participation in MTI-107.
- 5. Treatment with other neurokinin-1 receptor (NK₁-R) antagonists (e.g., aprepitant, fosaprepitant, rolapitant) within 4 weeks prior to enrollment.
- 6. Treatment with strong cytochrome P450 3A4 inhibitors within 4 weeks prior to enrollment (Appendix B).
- 7. Currently pregnant or breastfeeding or planning to become pregnant during the study.

5 STUDY DRUG

5.1 Study Drug Supply, Route of Administration, and Storage

The study drug in this study is seriopitant 5 mg in a film-coated tablet formulation for oral administration. The seriopitant tablets contain microcrystalline cellulose, mannitol, croscarmellose sodium, silicon dioxide, sodium lauryl sulfate, and magnesium stearate, and are film coated with Opadry[®] Brown.

The study drug will be provided in bottles that can be stored at room temperature (59-86°F, 15-30°C).

Each bottle will each contain 18 serlopitant tablets.

Additional details regarding study drug supplies can be found in the Pharmacy Manual.

5.2 Labeling and Study Drug Accountability

The study drug will be appropriately packaged and labeled in bottles with 18 tablets per bottle. The study drug supplied for this study is not to be used for any purpose other than this study, and study drug accountability must be maintained for all bottles distributed to the investigative site.

Additional details regarding study drug labeling and accountability can be found in the Pharmacy Manual.

5.3 Dosing Regimen

During the treatment period, subjects will take one seriopitant 5 mg tablet once daily orally. Subjects will be instructed to take all doses from Baseline Visit (Study Day 1) until the Week 52 Visit, once a day. Study drug may be taken with or without food.

Should the study drug be withheld (without intent to discontinue study drug, Section 5.6), the drug may be resumed at the discretion of the investigator, at the same dosing regimen.

5.4 Dose Modification

No dose modification of study drug will be allowed during this study.

5.5 Missed or Delayed Doses

Each dose of study drug after the first dose must be administered once daily. If a dose is missed, that dose will be considered and documented as a missed dose. Dosing should resume as directed the next day.

5.6 Study Drug Discontinuation

Subjects should be discontinued from study drug in the following situations:

- Any medical condition that may jeopardize the subject's safety if study drug is continued, in the investigator's and/or Sponsor's opinion; this may include the development of persistently (2 successive occasions) abnormal thyroid function tests (TSH >10, or TSH > 6 with low free T4; TSH <0.1, or TSH < 0.35 with high free T4); abnormal morning prolactin, cortisol, or corticotropin levels; or signs and symptoms of adrenal insufficiency
- Baseline serum creatinine, total bilirubin, alanine aminotransferase (ALT) or aspartate aminotransferase (AST) > 2.5 times the upper limit of normal (ULN) (exception may be made for retesting within 28 days of enrollment as approved by the Medical Monitor)
- A female subject desires to become pregnant at the current time, stops contraception or expels her intrauterine device/implant, or becomes pregnant
- A female subject has new breast findings (e.g. a palpable mass or abnormal mammography, discharge), or has abnormal vaginal discharge or bleeding

- The subject decides to discontinue study drug, or withdraws consent from the study
- The subject reports use of a strong CYP3A4 inhibitor (as listed in Appendix B) within 4 weeks of the study visit at which it was reported, initiates any investigational medication, or other NK₁-R antagonist (exception may be made for use of approved NK₁-R antagonist for less than 5 continuous days)
- Discontinuation is deemed to be in the best interest of the subject, in the investigator's and/or Sponsor's opinion, including evidence that the subject does not meet inclusion/exclusion criteria intended primarily for safety reasons, or a persistent lack of adherence to study procedures

The Sponsor or designee should be contacted within 24 hours of investigator's awareness of any study drug discontinuation due to an AE or pregnancy. Investigators should make every effort to contact the Sponsor or designee before discontinuing study drug, if possible.

Subjects who discontinue study drug prior to completing the treatment period will enter a 5-week follow-up period following the last dose of study drug (Section 6.4.10). Every effort should be made for subjects to complete this follow-up visit after a subject has discontinued from study drug.

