5.7.1 Excluded Therapies

The following therapies and activities are excluded from the Baseline visit through the follow-up period:

- NK₁-R antagonists (other than study drug, exception may be made for use of approved NK₁-R antagonist for less than 5 continuous days)
- Strong CYP3A4 inhibitors (See Appendix B; exceptions may be made for use within 4 weeks of the study visit at which it was reported)
- Any investigational drug therapy other than serlopitant

Use of any excluded therapies should be reported as soon as possible, and will be recorded as protocol deviations for subjects who receive them. Subjects may be discontinued from the study drug (Section 5.6).

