APPENDIX B LIST OF STRONG CYP3A4 INHIBITORS

The list of strong CYP3A4 inhibitors is based on the United States Food and Drug Administration (FDA) list effective September 26, 2016, *Examples of clinical inhibitors for P450-mediated metabolisms (for concomitant use clinical DDI studies and/or drug labeling* ("Examples of clinical inhibitors for P450-mediated metabolisms (for concomitant use clinical DDI studies and/or drug labeling (9/26/2016)").

Note: This Appendix may be replaced if applicable (e.g., if updated by the FDA) through site communications without requiring a protocol amendment.

- 1. boceprevir
- 2. clarithromycin
- 3. cobicistat
- 4. conivaptan
- 5. danoprevir and ritonavir
- 6. diltiazem
- 7. elvitegravir and ritonavir
- 8. idelalisib
- 9. indinavir and ritonavir
- 10. itraconazole^a
- 11. ketoconazole^a
- 12. lopinavir and ritonavir
- 13. nefazodone
- 14. nelfinavir
- 15. paritaprevir and ritonavir and (ombitasvir and/or dasabuvir)
- 16. posaconazole^a
- 17. ritonavir
- 18. saquinavir and ritonavir
- 19. telaprevir
- 20. tipranavir and ritonavir
- 21. troleandomycin
- 22. voriconazole^a
- 23. regular grapefruit juice consumption (note: The effect of grapefruit juice varies widely among brands and is concentration-, dose-, and preparation-dependent. Grapefruit juice may be a strong or a moderate CYP3A inhibitor depending on the preparation)^b
- ^a When administered topically, it may not be considered a strong CYP3A4 inhibitor due to limited systemic absorption.
- ^b The occasional consumption of grapefruit juice or the consumption of grapefruit or other citrus fruits (e.g., pomelo, lemon, lime, Seville orange, bitter orange, starfruit) is not contraindicated.

с

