#### 2. INTRODUCTION

The MTI-107 study described herein is an open-label study to assess the long-term safety of serlopitant in adults with pruritus associated with prurigo nodularis (PN), atopic dermatitis (AD), or psoriasis.

Subjects enrolled in MTI-107 may have or may not have participated in previous Menlo Therapeutics Inc. studies. Previous study participation includes studies in PN (MTI-105, MTI-106, TCP-102), in AD (MTI-103) and in psoriasis (MTI-109).

The MTI-107 study has been terminated early by Sponsor. The Statistical Analysis Plan has been updated to facilitate an abbreviated clinical study report.

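### Protocol v3.0 Sections 5.6 and 5.7.1 disagree on a report of strong CYP3A4 inhibitor use: the same 4-week condition calls for stopping study drug in one and allows an exception in the other

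*Protocol*

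**What the plan says.** Section 5.6 of protocol v3.0 opens "Subjects should be discontinued from study drug in the following situations". One of its bullets covers the subject who "reports use of a strong CYP3A4 inhibitor (as listed in Appendix B) within 4 weeks of the study visit at which it was reported". That bullet also covers starting an investigational medication or another NK1-R antagonist. Its only exception is for an approved NK1-R antagonist taken for less than 5 continuous days. A separate bullet, on raised baseline laboratory values, has its own exception and names who approves it: "exception may be made for retesting within 28 days of enrollment as approved by the Medical Monitor". The section later adds: "Investigators should make every effort to contact the Sponsor or designee before discontinuing study drug, if possible".

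Section 5.7.1 lists strong CYP3A4 inhibitors among the therapies excluded from the Baseline visit through follow-up, and then says "exceptions may be made for use within 4 weeks of the study visit at which it was reported". It requires use of an excluded therapy to be recorded as a protocol deviation, and ends with "Subjects may be discontinued from the study drug (Section 5.6").

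Three other places bear on the point. Section 5.3 lets study drug be withheld, without intent to discontinue it, and resumed at the investigator's discretion. Appendix B defines which products count, with notes such as "When administered topically, it may not be considered a strong CYP3A4 inhibitor due to limited systemic absorption". SAP Section 6.3 says that protocol deviations will be shown in a data listing. The SAP introduction also states: "The MTI-107 study has been terminated early by Sponsor".

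**The concern.** One condition carries two consequences. In Section 5.6 it is a reason to stop study drug; in Section 5.7.1 it is a reason to allow the inhibitor by exception. Two sites faced with the same report could act differently and each point to the protocol.

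The rule is safety-relevant. Section 1.2.1 says serlopitant is metabolized by CYP3A4, the primary objective is long-term safety, and about 120 sites may enroll. The choice between the two sections decides who stays on serlopitant while using, or shortly after using, a strong inhibitor, and so whose adverse events and exposure days enter the safety summaries under that condition. Unless the rule that was applied is reported, a reader of the study report cannot tell whether subjects with such use stayed in by design, by local choice or in departure from Section 5.6.

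**Working it through.** No figure is stated and no arithmetic applies. The check is a comparison of text.

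| Element | Section 5.6 | Section 5.7.1 |
|---|---|---|
| Therapy | Strong CYP3A4 inhibitor, per Appendix B | Strong CYP3A4 inhibitor, per Appendix B |
| Time condition | Within 4 weeks of the reporting visit | Within 4 weeks of the reporting visit |
| Role of that condition | Reason to stop study drug | Ground for an exception |
| Verb for discontinuation | should | may, with a pointer to 5.6 |
| CYP3A4 exception | None | Yes |
| NK1-R antagonist exception | Less than 5 continuous days | Less than 5 continuous days |

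1. *Same condition.* The 4-week phrase is word for word the same in both sections, so they address the same report.

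2. *Mismatch specific to CYP3A4 inhibitors.* The NK1-R antagonist exception appears in both sections with the same limit. The CYP3A4 exception appears only in 5.7.1.

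3. *Possible site actions.* Stopping study drug satisfies both sections. Continuing under the 5.7.1 exception departs from 5.6. Withholding and resuming under 5.3 is a third route; 5.3 cross-refers to 5.6 but does not mention CYP3A4 inhibitors or say whether a hold satisfies 5.6.

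4. *Does other text settle it?* Appendix B says which products count, not when an exception applies. The sponsor-contact sentence in 5.6 concerns contact before stopping, not continuing under an exception. Section 8.1 names excluded therapy use in its title but gives no rule for it. SAP Section 6.3 provides for display of deviations, not for a decision.

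5. *Who decides?* Sections 5.6 and 5.7.1 contain three kinds of exception: laboratory retest, short NK1-R antagonist use, and CYP3A4 inhibitor use. Only the laboratory retest names an approver (the Medical Monitor), so 1 of 3 does. The gap is therefore not special to CYP3A4 inhibitors.

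6. *Supplied protocol versions.* The same pair of sentences stands in v1.0, v1.1, v2.0 and v3.0. This shows only that no supplied version gave sites a single rule.

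7. *What the planned outputs can show.* The index in SAP Section 10 names no deviation listing; Listing 16.2.2.1 covers eligibility criteria only. A count of subjects who continued could be attempted from medication dates (Listing 16.2.4.4.2), visit dates (16.2.5.1) and date of last dose (16.2.1.1), with four limits:
   - The medication listing has no field for the reporting visit or for an exception. The visit would have to be assumed, for example as the first visit on or after the medication start date.
   - Listing 16.2.1.1 gives one first-dose and one last-dose date. A subject held and resumed under 5.3 would look like one who never stopped. Listing 16.2.5.2 gives tablets used per bottle, not dates of interruption.
   - The medication shell itself shows a partial start date and a blank end date. SAP Section 6.1.5 has a default for on-treatment status but none for placing such records in a 4-week window.
   - Regular grapefruit juice consumption is in Appendix B, and nothing shows that it would be recorded in a listing of coded medications.

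**The case against.** The best defence is that the sections form a default plus an exception. *Should* is weaker than *must*, 5.7.1 supplies the discretion, and 5.6 merely fails to repeat it. Section 5.7.1 also runs through follow-up, when there is no study drug to stop, so its exception has some scope of its own.

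Part of this stands. The sections are not two commands that cannot both be obeyed, because a site that stops study drug obeys both. The follow-up scope is also real, but it leaves the on-treatment period unresolved. The default-plus-exception reading does not close the gap. Where the authors wanted an exception in 5.6 they wrote it there, as for the laboratory retest and the NK1-R antagonist. And 5.7.1 sends the reader back to 5.6 for the consequence, where *may* becomes *should*.

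Two further objections have force. Since the study was terminated early, rewording the protocol cannot change what sites did. And repetition across four protocol versions, three of them superseded, is not a measure of effect. Both points bear on how much weight the inconsistency carries and on where the remedy should lie, not on whether it exists.

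A reader might also infer that subjects were in fact handled inconsistently, or were over-exposed. The documents do not support that: they report no such use, no exceptions granted and no exposure change with an inhibitor.

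**Conclusion.** The inconsistency is real and concerns wording rather than a design choice. Protocol v3.0 attaches a stopping instruction and a permitted exception to the same 4-week report of strong CYP3A4 inhibitor use, leaves the status of a temporary hold open, and does not say who decides. It rests on the text alone; no statistical assumption is needed.

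Its size cannot be stated. The number of subjects with such use and the change in serlopitant exposure are not in the documents and are not estimated. It should be corrected and reported, but nothing here shows that any safety result is wrong. Nor should a reader infer that an exact count of continued subjects, or of exceptions granted, can be read from the planned medication, visit and last-dose listings. Any such count is approximate and counts subjects not permanently stopped. This review takes no position on which clinical rule is right.

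**What to change.** *Protocol text.* Reconcile Sections 5.6 and 5.7.1, and state how a hold under 5.3 relates to them, so that one report leads to one instruction. Name who decides any exception. The choice of rule belongs to the sponsor. Cost: about one sentence in each of 5.6 and 5.7.1 and a clause on 5.3. With the study terminated, this serves the record and any protocol that reuses the text.

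*Study report.* State which rule was applied. Report subjects with strong CYP3A4 inhibitor use from the deviation records that 5.7.1 requires. Add the deviation listing promised in SAP Section 6.3 to the index in SAP Section 10. Cost: one listing and one short statement, using records the protocol already requires.

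*If a count of subjects who continued is also derived* from Listings 16.2.4.4.2, 16.2.5.1 and 16.2.1.1, label it approximate and state its limits: assumed reporting visit, temporary interruptions not shown, possible partial dates, and grapefruit juice possibly not captured.
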